## **7.2 Analysis Populations**

### **7.2.1 Enrolled Population**

The Enrolled Population is defined as all screened patients excluding screen failures.

### **7.2.2 Intent-to-Treat (ITT) Population/Safety Population**

The ITT/Safety Population will include all patients who have received at least 1 dose of APX001.

### **7.2.3 Modified Intent-to-Treat (MITT) Population**

The MITT Population will include all patients who satisfy the following criteria:

- Receive at least 1 dose of study drug;
- Have a confirmed diagnosis of candidemia and/or invasive candidiasis caused by *C. auris* within 120 hours (for candidemia) or 168 hours (for invasive candidiasis without candidemia) of study qualification (as determined by the DRC)

### **7.2.4 Per-Protocol (PP) Population**

The PP Population will include all patients in the MITT Population who satisfy the following criteria:

- Meet the protocol's key inclusion and exclusion criteria;
- Receive at least 80% of the intended doses;
- Have no major protocol violations.

Based on the above criteria, the validity listings will be provided to identify which patients to be excluded from the PP Population. After the study team's review, the decision to exclude a patient from the PP Population will be finalized and documented.

The analysis based on PP Population specified in the following sections will be performed only if MITT and PP Population are not identical.

### **7.3 Patient Data and Study Conduct**

#### ***7.3.1 Patient Disposition***

Patient disposition will be summarized for the ITT/Safety Population and MITT Population in total. The following patient disposition categories will be included in the summary:

- Patients who received study drug;
- Patients who did not receive study drug;
- Patients who completed the study drug;
- Patients who did not complete the study drug (and reason);
- Patients who did not complete the study drug due to COVID-19;
- Patients who completed the study;
- Patients who did not complete the study (and reason); and
- Patients who did not complete the study due to COVID-19.

For patients who did not complete study drug and patients who did not complete study, a summary will be provided by reason of discontinuation. In addition, the total number of patients for each defined population will be tabulated.

#### ***7.3.2 Protocol Deviations***

The number of patients with at least one reportable protocol deviation, and the number of patients with at least one reportable deviation in each deviation category defined in the study protocol deviation plan will be presented in total based on the ITT/Safety Population and MITT Population. In addition, the protocol deviations related to COVID-19 will be categorized and summarized separately.

In addition, number of patients with visits not completed, in-person partially completed, and performed virtually due to COVID-19 will be summarized for the ITT/Safety Population. The number of patients with visits performed out of window due to COVID-19 will also be tabulated.

Protocol deviations will also be listed by patient.

### **7.3.3 Demographic and Baseline Characteristics**

The following demographic and baseline characteristics will be summarized:

- Age (years) and age categories (<65 years,  $\geq$ 65 years);
- Sex;
- Childbearing potential;
- Race;
- Ethnicity;
- Height (cm);
- Weight (kg);
- Body mass index (BMI) (kg/m^2) ;
- APACHE II score and categories (<10, 10-19, 20-30, or  $\geq$ 30); and
- ICU vs. non-ICU.

Demographic and Baseline characteristics will be summarized with descriptive statistics or counts and percentages of patients as appropriate in total for the ITT/Safety Population, MITT, and PP Populations.

### **7.3.4 Baseline Infection Characteristics**

All baseline pathogens will be summarized with counts and percentages of patients in total for the MITT and PP Populations.

Details of organism identification and antifungal susceptibility results including MICs of all antimicrobials tested will be listed by patient. Both data from local and central microbiological laboratories will be listed.

### **7.3.5 Medical History**

The primary underlying condition leading to candidemia and other medical history will be coded to system organ class and preferred term using the Medical Dictionary for Regulatory Activities (MedDRA, Version 22.0). Counts and percentages of patients with medical history by system organ class and preferred term will be summarized in total based on the ITT/Safety Population and MITT Population.

All medical history will be listed by patient.

### **7.3.6 Prior and Concomitant Medications**

Prior and Concomitant medications will be coded to anatomical therapeutic chemical (ATC) class and preferred term using the World Health Organization (WHO) Drug Dictionary (March 2019G B3 Version).

Prior medications are medications used before the first dose of study drug. Concomitant medications are medications that were taken on or after first dose of study drug.

The number and percentages of patients who receive the following prior and concomitant medications will be summarized by ATC class and preferred term in total for the ITT/Safety Population and MITT Population:

- Prior medications;
- Concomitant medications;
- Prior systemic antifungals; and
- Concomitant systemic antifungals.

All prior and concomitant medications and procedures will be listed by patient.

### ***7.3.7 Study Drug Exposure and Compliance***

Study drug includes both intravenous and oral dose. Days of exposure to study drug will be calculated as the last dose date of study drug – first dose date of study drug + 1. Overall days of exposure to study drug will be summarized in total based on the ITT/Safety and MITT Populations with descriptive statistics and with counts and percentages of patients with exposure in the following categories:

- $\leq 14$  days
- $>14$  to  $\leq 28$  days
- $>28$  to  $\leq 42$  days
- $>42$  days

For patients who switch from intravenous to oral dose, the compliance rate for oral dose will be calculated as the total amount of doses received divided by the total amount of doses expected then multiplied by 100. The total amount of expected doses is the number of medication days multiplied by the expected doses per day. Number of medication days is the total number of days from the date of the first oral dose of study drug to the date of the last oral dose of study drug.

Percent compliance with oral study drug will be calculated using the following formula:

$$\% \text{compliance} = \frac{\text{total amount of doses received} * 100}{\text{expected doses per day} * \text{total number of medication days}}$$

The compliance rate for oral dose will be summarized with descriptive statistics in total for the ITT/Safety and MITT Populations. In addition, contingency tables will be provided to show the number and percentage of patients in each treatment group with compliance in the following categories:  $<80\%$  and  $\geq 80\%$ .

### **7.4 Efficacy Assessment**

The efficacy analysis will be performed based on MITT Population. The analysis will be repeated on PP Population if MITT and PP Population are not identical.

#### **7.4.1 Primary Efficacy Endpoints**

The primary efficacy parameter is percentage of patients with Treatment Success at EOST as determined by the DRC.

The number and percentage of patients with Treatment Success or Treatment Failure at EOST determined by the DRC will be summarized descriptively in total for the MITT Population. The 95% two-sided exact binomial confidence interval of the treatment success rate will also be presented.

Additional analyses of the primary efficacy endpoint will be performed for the PP Population in the same manner.

#### **7.4.2 Secondary Efficacy Endpoints**

Descriptive statistics will be provided for secondary efficacy endpoints as the following.

##### **7.4.2.1 Treatment Outcome**

Number and percentage of patients in the MITT and PP Populations with treatment outcomes (Treatment Success Sustained, Clinical Relapse, and Other [Non-Relapse]) at 2 and 4 weeks after EOST as determined by the DRC will be presented descriptively, along with the 95% two-sided exact binomial confidence interval for the sustained treatment success rate.

Number and percentage of patients in the MITT and PP Populations with treatment outcomes (Treatment Success and Treatment Failure) at EOST as determined by the Investigator will be tabulated, along with the 95% two-sided exact binomial confidence interval.

Number and percentage of patients in the MITT and PP Populations with Sustained Treatment Success at 2 and 4 weeks after EOST as determined by the Investigator will be tabulated, along with the 95% two-sided exact binomial confidence interval.

##### **7.4.2.2 Mycological Outcome**

The number and percentage of patients in the MITT and PP Populations with Eradication and Presumed Eradication at EOST will be summarized descriptively, along with the 95% two-sided exact binomial confidence interval.

The number and percentage of patients in the MITT and PP Populations with Recurrence at 2 and 4 weeks after EOST will be summarized descriptively.

##### **7.4.2.3 Time to First Negative Blood Culture**

Time to first negative blood culture is defined as the number of days from first dose date of study drug to the date of first negative blood culture plus 1.

Time to first negative blood culture will be summarized in total using descriptive statistics for the MITT and PP Population.

In addition, the Kaplan-Meier estimate of the median time to first negative blood culture and the associated 95% confidence interval will be presented. Patients without a negative blood culture at post-baseline visits will be censored at the last assessment date.

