On Study Day 1 (or over the first 24 hours if dosing starts in the evening), a 1000 mg APX001 loading dose will be administered over 3 hours by IV infusion twice daily (BID). On Study Days 2 and 3, a 600 mg APX001 maintenance dose will be administered over 3 hours by IV infusion once daily (QD). On Study Day 4 and onward, the APX001 maintenance dose will be administered as either 600 mg APX001 IV infusion QD over 3 hours or 800 mg PO QD. Patients who have completed a minimum of 3 days of IV APX001, are clinically stable as determined by the Investigator, and are able to swallow tablets, may switch from IV to PO dosing on Study Day 4 and onward. Study drug will be administered for 14 days after clearance of *Candida* organisms from the bloodstream (two consecutive negative blood cultures), and in accordance with clinical judgment as applicable for other infected sites, up a maximum of 42 days.

Patients will be monitored by daily blood culture from signing informed consent, through dosing, during Study Drug Treatment until 2 consecutive blood cultures are negative for *Candida* spp., at EOST, and at 2 and 4 weeks after EOST, or Early Termination. For patients diagnosed with invasive candidiasis, relevant cultures, histopathology, and imaging tests to assess the site(s), extent, progress, and outcome of the *Candida* infection will be conducted as clinically indicated. All results should be recorded in the electronic Case Report Form. The management of intravascular catheters, intravascular devices, and, if applicable, any drains will be recorded, including any associated microbiology results.

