6.4.2 Study Drug Treatment (\leq 6 Weeks)

Day 1 dose

Prior to the initiation of the first APX001 dose, a diagnosis of candidemia and/or invasive candidiasis caused by *C. auris* (in a single or mixed *Candida* spp. infection) must be confirmed within 120 hours (for candidemia) or 168 hours (for invasive candidiasis without candidemia) of formal qualification for the study. The initiation of the first dose of APX001 must occur within 12 hours of qualification for the study.

- Study drug to be administered as a 3-hour IV loading dose BID on Day 1 (or over the first 24 hours if started in the evening).

Day 2 onwards (maximum to Day 42)

- On Study Days 2 to 3, study drug to be administered over 3 hours by IV QD; on Day 4 and onward, oral administration of the study drug may be considered if the patient meets the IV to oral switch criteria
- Study drug to be administered for a minimum of 14 days after clearance of *Candida* organisms from the bloodstream or other infected sites,
- Maximum duration of study drug treatment is up to 6 weeks total (42 days, inclusive of the loading dose [Study Day 1])

The following procedures will be performed during the period of Study Drug Treatment:

- For patients with candidemia (with or without invasive candidiasis) **daily** blood cultures are to be performed on Days 1 through 4 (minimum), continuing until 2 negative blood culture results are reported from 2 consecutive samples. (Considered negative at least 48 hours after collection).
- For patients with invasive candidiasis, with or without candidemia, appropriate material from the infected site(s) is to be sampled for culture or histopathology to monitor the progress of infection, as clinically indicated until mycological and/or clinical resolution.
- Imaging tests are to be performed as clinically indicated to monitor the site(s), extent and progress of invasive candidiasis infection
- Intravascular catheter management log; all changes are to be recorded until EOST while inpatient, and as clinically indicated thereafter or for outpatients
- Daily vital signs, including temperature, blood pressure, heart rate, respiratory rate, oxygen saturation, and weight while an inpatient. Measurements are to be continued twice weekly while on treatment as an outpatient.

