7.5 Microbiological Assessments

7.5.1 Blood Cultures

For patients with candidemia, *Candida auris* confirmed in blood culture is required for qualification into the study, which must occur within 120 hours of the collection of the indicative positive blood sample. The study site's local microbiology laboratory will analyze blood and other cultures for *Candida* spp. Isolates of all *Candida* spp from SOC eligibility cultures must be submitted to the mycology reference laboratory for confirmation of identification and susceptibility testing.

For all patients (candidemia or invasive candidiasis), once consent is obtained, the first blood collection should comprise two consecutive sets (1 aerobic and 1 anaerobic blood culture bottle in each set) of blood cultures from 2 separate IV sites (1 from a central venous catheter (CVC) and 1 peripheral, or 2 peripherals if CVC is not applicable); a minimum of 1 set (1 aerobic and 1 anaerobic blood culture bottle in each set) of blood cultures is required thereafter.

Blood cultures for *Candida* spp. will be performed during the Screening period (daily), at Baseline (pre-dose), during Study Drug Treatment, at EOST, and 2 and 4 weeks after EOST, or Early Termination. During the Study Drug Treatment Period, blood cultures are required daily on Study Days 1 through 4; thereafter, blood cultures during study drug treatment may be stopped after negative results on 2 consecutive blood culture tests are obtained.

The study site's local microbiology laboratory will analyze all blood cultures for *Candida* spp. The local microbiology lab will send all *Candida* isolates from blood cultures to the mycology reference laboratory for confirmation of identification and susceptibility testing.

In the event that the study site uses a rapid diagnostic test for the diagnosis of candidemia, subsequent confirmatory blood cultures are required, and resulting isolates should be submitted to the mycology reference laboratory for confirmation of identification and susceptibility testing. Results from rapid diagnostic tests performed must be captured in the eCRF.

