- j. Screening laboratory assessments to determine eligibility will be performed at the local laboratory and may have been collected as SOC within the previous 24 hours. Laboratory assessments collected after Screening will be sent to the central laboratory for analysis. Clinical safety laboratory assessments (serum chemistry [including testing for C-reactive protein], hematology, coagulation, and urinalysis) will be collected at Baseline (pre-dose), twice weekly during Study Drug Treatment, at EOST, and 2 and 4 weeks after EOST, or Early Termination. If clinically indicated and at the discretion of the Investigator, or if a suspected adverse event is identified, clinical laboratory assessments may be conducted at any time during the study and compared to Baseline.
- k. Urine pregnancy test (for females of childbearing potential only) every 30 days if required by local regulations.
- l. A complete physical examination will be conducted at Baseline (pre-dose). Complete physical examination will include an assessment of general appearance, skin, eyes, heart, chest, abdomen, the body site that corresponds to the entry site of candidemia (e.g. central venous catheter entry site) and/or site of invasive candidiasis, if applicable, and a neurological examination. Components of the neurological examination include cranial nerve, sensory and motor examination, reflex and gait testing, and coordination assessment. A neurological examination will be performed twice weekly during study drug treatment. A focused, symptom-based physical examination will be performed once weekly during study drug treatment, EOST, and 2 and 4 weeks after EOST, or Early Termination.
- m. Blood cultures (daily) during 120-hour (5-day) screening period: after consent obtained the first blood collection to comprise two sets taken at one time, within 120 hours before the initiation of APX001 study treatment; 1 set thereafter.
- n. All *Candida* spp. isolates must be submitted to the mycology reference laboratory for confirmation of identification and susceptibility testing.
- o. During Study Drug Treatment, daily blood cultures on Study Days 1 through 4 (minimum), continuing daily until 2 negative blood culture results on 2 consecutive tests reported.
- p. Optional rapid diagnostic test, if available, for *Candida* diagnosis; test (e.g. T2MR or PCR); subsequent confirmatory blood cultures must also be performed.

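### Time to first negative blood culture includes patients with no candidemia to clear and censors those who die uncleared

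*SAP*

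**What the plan says.** SAP 7.4.2.3 counts days from first dose to first negative blood culture, plus one. It gives the analysis set as: "Time to first negative blood culture will be summarized in total using descriptive statistics for the MITT and PP Population". A Kaplan-Meier median with a 95% confidence interval is added. The only censoring rule is: "Patients without a negative blood culture at post-baseline visits will be censored at the last assessment date". Death is not mentioned.

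SAP 7.2.3 sets the MITT diagnostic window at 120 hours "for candidemia) or 168 hours (for invasive candidiasis without candidemia) of study qualification (as determined by the DRC"), so it expressly admits patients without candidemia. SAP 7.2.4 builds on this: "The PP Population will include all patients in the MITT Population who satisfy the following criteria". Its criteria concern eligibility, dosing and violations, not candidemia.

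The documents differ on who has daily on-treatment blood cultures:

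- The Protocol Synopsis, Protocol 3.1 and SAP 2.2 set no candidemia condition: "Patients will be monitored by daily blood culture from signing informed consent, through dosing, during Study Drug Treatment".
- Protocol 7.5.1 and SAP 6.4.3.1 also set none: "During the Study Drug Treatment Period, blood cultures are required daily on Study Days 1 through 4". Footnote o of Protocol Appendix A and of SAP Table 1 agrees: "During Study Drug Treatment, daily blood cultures on Study Days 1 through 4 (minimum").
- Protocol 6.4.2 alone opens its daily-culture instruction with "For patients with candidemia (with or without invasive candidiasis").

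**The concern.** A patient with invasive candidiasis and sterile blood has no bloodstream infection to clear, yet the definition gives that patient a clearance time. What that time measures is the culture schedule. On daily cultures from Day 1 it is about Day 1 or 2, close to the minimum. If a site follows Protocol 6.4.2, the first on-study negative may not come until the end of treatment.

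Death is a separate problem. A patient who dies culture-positive can never clear. Kaplan-Meier censoring assumes that the patient would have gone on to clear like those still under observation. The Protocol introduction calls these infections highly lethal, so such deaths are foreseeable.

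A smaller point concerns living patients who fail or switch antifungals. Protocol 4.4 and SAP 7.4.2.5 then follow them only for survival or safety, so their censoring may also be informative. The SAP does not ask how many there are.

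Readers will take the Kaplan-Meier median as time to bloodstream clearance, and a single total-column summary does not let them recover the candidemia-only result.

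**Working it through.** The plan has no figure to reproduce: about 15 patients, no formal sample-size calculation, and no expected clearance time, case mix or death rate. Every input below is assumed. The median is the first day on which estimated clearance reaches 50%.

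**Population.** Take 10 candidemic patients clearing on Days 2, 3, 3, 4, 5, 5, 6, 7, 9 and 12. By Day 4, 4/10 = 40% have cleared; by Day 5, 6/10 = 60%. The median is Day 5 (95% CI 3 to 7 with a linear interval, 2 to 7 with log-log). Then add k patients without candidemia:

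| k added | 0 | 1 | 2 | 3 | 4 | 5 |
|---|---|---|---|---|---|---|
| Scored Day 1 or 2 (schedule in most sections) | 5 | 5 | 4 | 4 | 3 | 3 |
| Scored Day 14, 28 or 42 (Protocol 6.4.2 alone) | 5 | 5 | 5 | 6 | 6 | 7 |

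For k = 5 scored early, (5 + 3)/15 = 53% have cleared by Day 3. Scored late, 7/15 = 47% by Day 6 and 8/15 = 53% by Day 7. Averaging at exact ties changes only k = 2 (4.5 and 5.5) and k = 4 (3.5 and 6.5).

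**Death.** Take 8 patients clearing on Days 2, 3, 4, 5, 6, 8, 10 and 12, plus 3 who die uncleared and are censored on Days 3, 4 and 5 (N = 11). Kaplan-Meier uses S(t) = ∏(1 − d/n):

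- Day 5: 10/11 × 9/10 × 7/8 × 5/6 = 0.597.
- Day 6: 0.597 × 3/4 = 0.447, so the median is Day 6.

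With death as a competing event and no other censoring, cumulative incidence is the number cleared divided by N: 5/11 = 45.5% on Day 6 and 6/11 = 54.5% on Day 8. The median is Day 8.

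Now place the deaths on every combination of censoring days from 1 to 12:

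| Uncleared deaths | Cumulative-incidence median | Combinations where Kaplan-Meier is shorter |
|---|---|---|
| 1 | 6 | 1 of 12 (Day 1) |
| 2 | 6 (exact tie at 50%) | 1 of 78 (both Day 1) |
| 3 | 8 | 161 of 364 |

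Kaplan-Meier was never longer. With three deaths it is shorter in 35 of 35 combinations with all three on Days 1 to 5, and in 0 of 84 with all three on Day 6 or later. These are counts of combinations, not probabilities.

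**Constant hazards.** With clearance rate λ and death rate μ, the Kaplan-Meier median is ln 2/λ. The cumulative-incidence median solves [λ/(λ+μ)]·[1 − exp(−(λ+μ)t)] = 0.5. The right-hand columns are for mean times to death of 15, 30 and 60 days:

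| Mean clearance | Kaplan-Meier median | Cumulative-incidence median | Die uncleared |
|---|---|---|---|
| 5 days | 3.5 | 4.1, 3.8, 3.6 | 25%, 14%, 8% |
| 10 days | 6.9 | 10.8, 8.2, 7.5 | 40%, 25%, 14% |

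**Both together.** Assume N = 15: 7 candidemic patients clear on Days 2, 3, 4, 5, 6, 7 and 9; 3 die uncleared with last cultures on Days 2, 3 and 4; 5 have no candidemia and are first negative on Day 1 or 2. The median is Day 4 under the SAP rule, Day 5 in candidemic patients with deaths censored, and Day 6 with deaths kept as not cleared. By Day 9 the candidemia-only Kaplan-Meier estimate is 100% cleared; the true cumulative incidence is 7/10 = 70%. The plain median of observed times is 2.5 in all patients against 5 in candidemic patients, so the descriptive summary is affected too.

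**The case against.** The strongest reply is that this is a secondary, descriptive endpoint in a single-arm study of about 15 patients, with no test, comparator or threshold. Deaths are failures in the primary endpoint (SAP 6.4.1) and are reported in SAP 7.4.2.4 and 7.4.2.5. The illustrated population shifts lie within the sampling interval. The share without candidemia is invented, and exclusion 13 removes several deep-seated infections. Exclusion 2 removes patients expected to live less than 7 days, which makes a cluster of very early deaths less typical. The step from Day 6 to Day 8 partly reflects assumed data with no clearance on Day 7. A sentence giving the number who died uncleared might inform readers nearly as well as a competing-risk estimate. On treatment failures, the SAP 7.4.2.5 sentence does not stop cultures, which are still due at the end of treatment or early termination.

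Most of this stands as a limit on size. The death error often leaves the median unchanged, and the point about failures supports no more than a reported count. None of it supplies the missing restriction: no section limits the endpoint to candidemia, and the general rules in SAP 7.1.2 set no event or censoring rule for it. A wide interval around the wrong quantity does not make it the right one, and reporting mortality separately does not correct the clearance curve.

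**Conclusion.** The concern holds and should be fixed. The population error follows directly from the SAP's wording. The death error follows from its only censoring rule, under which one minus Kaplan-Meier equals or exceeds true cumulative clearance on any culture schedule. The direction of the population error does depend on the schedule: on the one most sections give, the median is equal or shorter; under Protocol 6.4.2 alone it can be longer.

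In the separate population and death examples, 5 of 15 patients without candidemia move the median by two days in either direction, 1 does not move it, and three early uncleared deaths among 11 shorten it by two days. Few or late deaths have little or no effect. Confidence is high in the defect; its size in this trial cannot be known from the documents.

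**What to change.** In SAP 7.4.2.3:

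1. Restrict the analysis to MITT and PP patients with candidemia at baseline. Add a sensitivity analysis in those whose last pre-dose blood culture was positive.
2. Treat death before a negative culture as a competing event, using Aalen-Johansen cumulative incidence with the median as the first day it reaches 50%. Name the confidence-interval method, and say how uncleared deaths enter the descriptive statistics.
3. Keep censoring for patients alive without a negative culture, and report how many were censored after treatment failure or a switch of antifungals. State whether the last assessment means the last blood culture or the last visit.
4. For clarity only, say in the definition that the negative culture is collected after the first dose. The censoring sentence, read with SAP 7.1.3, already implies it.

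Reconcile Protocol 6.4.2 with the Protocol Synopsis, 3.1, 7.5.1 and Appendix A, and with SAP 2.2, 6.4.3.1 and Table 1, on which patients have daily on-treatment blood cultures.

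The cost is SAP wording and minor programming on data already collected, plus one schedule clarification. SAP Section 1 has the plan finalised before database lock, so the rule can be set in advance. The drawback is a smaller n for this endpoint, and smaller still in the sensitivity analysis.

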### **7 STATISTICAL METHODOLOGY**

#### **7.1 General Considerations**

##### **7.1.1 *Summary Statistics***

Summary statistics will be presented in total. For continuous variables, the number of observations (n), mean, standard deviation, median, minimum, and maximum will be provided. For categorical variables, the frequency and percentage in each category will be displayed.

For summary statistics, the mean and median will be displayed to one decimal place greater than the original value and the measure of variability (e.g. standard deviation) will be displayed to two decimal places greater than the original value.

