### **7.1.2 Handling of Dropouts and Missing Data**

Subjects who dropped out or had missing outcome data will be included in the denominator for efficacy analyses. A clinical failure occurring at an earlier time point will be carried forward to the subsequent visits.

In cases of missing or incomplete dates (e.g. Adverse event [AE] and concomitant medications), the missing component(s) will be assumed as the most conservative value possible. For example, AEs with missing start dates, but with stop dates either overlapping into the treatment period or missing, will be counted as treatment-emergent, taking the worst-case approach. When partial dates are present in the data, both a partial start date and/or a partial stop date will be evaluated to determine whether it can be conclusively established that the AE started prior to the start of study drug or ended prior to the start of study drug. If the above cannot be conclusively established based on the partial and/or present dates, then the AE will be considered as treatment-emergent. Actual data values as they appear in the original eCRF will be presented in the data listings.

Missing values for other variables will not be imputed and only observed values will be used in data analyses and summaries.

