#### **7.4.2.5 DRC Assessments**

Reasons for EOST failure according to DRC classifications (i.e. because (i) Blood cultures and/or cultures from other sites did not become negative at EOST, (ii) *Candida* infection spread to other sites, (iii) Additional antifungals given, (iv) Patient died, (v) Patient withdrew from study but did not die, or (vi) Other), will be summarized descriptively at the EOST visit for the MITT and PP populations. Once a patient has failed treatment, they are subsequently evaluated only for survival and for relevant safety parameters.

Reasons for relapse, or other reasons for not having an outcome of sustained success at follow-up according to DRC classifications, will be summarized descriptively at 2 and 4 weeks after EOST for the MITT and PP populations. Once a patient has relapsed, or has been assessed as a non-sustained success for any reason, they are subsequently evaluated only for survival and for relevant safety parameters.

Reasons for death according to DRC classifications (i.e. Candidemia/invasive candidiasis probably contributory, candidemia/invasive candidiasis probably not contributory, or not known) will be tabulated for the MITT and PP populations.

Factors that can affect outcome, such as intravascular catheter management (timely removal of lines), will be also be summarized descriptively.

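### The mean/SD/median planned beside the Kaplan-Meier estimate of time to first negative blood culture describes only patients who cleared, yet is labelled MITT and PP

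*SAP*

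**What the plan says.** SAP 7.4.2.3 takes the endpoint as "defined as the number of days from first dose date of study drug to the date of first negative blood culture plus 1". It then plans two summaries.

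- **Ordinary descriptive statistics.** "Time to first negative blood culture will be summarized in total using descriptive statistics for the MITT and PP Population". SAP 7.1.1 gives the content: "For continuous variables, the number of observations (n), mean, standard deviation, median, minimum, and maximum will be provided". SAP 7.1.2 gives the general rule for absent values: "Missing values for other variables will not be imputed and only observed values will be used in data analyses and summaries".
- **A time-to-event estimate.** "In addition, the Kaplan-Meier estimate of the median time to first negative blood culture and the associated 95% confidence interval will be presented". For patients who do not clear: "Patients without a negative blood culture at post-baseline visits will be censored at the last assessment date".

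Failure to clear also appears in SAP 7.4.2.5, where one Data Review Committee (DRC) reason for failure at end of study drug treatment (EOST) is "Blood cultures and/or cultures from other sites did not become negative at EOST". Protocol 9.2.1.2 promises only a descriptive summary of this endpoint and names no statistic.

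**The concern.** The second summary treats the endpoint as censored. The first does not. A patient without a negative culture has no date from which to compute a time, so on the observed-values rule that patient contributes nothing to the mean, SD or median. Those figures then describe the patients who cleared, although the SAP assigns them to the MITT and PP populations. If censoring times were entered instead, days on which a patient was still uncleared would count as clearance days. The SAP does not say which applies; the observed-values rule points to the first.

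Two medians for one endpoint may therefore be reported under the same population label, answering different questions. In a single-arm study of about 15 patients, the shorter one could be quoted for speed of clearance, although it carries almost no information about how many patients cleared.

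**Working it through.** The documents give no clearance rate, non-clearance rate or expected median, so there is no planned figure to reproduce. Only the sample size of about 15 (SAP 5) comes from them. All clearance and censoring times below are assumptions.

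**1. Worked example, 15 patients.** Nine clear, on days 1, 2, 2, 3, 3, 4, 4, 5, 6. Six never clear and have last cultures on days 6, 8, 9, 10, 12, 14.

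Ordinary summary, observed values only (n = 9):
- Mean = (1+2+2+3+3+4+4+5+6)/9 = 30/9 = 3.3 days.
- Median = 5th of 9 ordered values = 3.0 days.

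Kaplan-Meier, all 15 patients. S(t) is the product over clearance days of (1 − number clearing/number at risk), and the median is the first day with S ≤ 0.5:

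| Day | At risk | Clear | S |
|---|---|---|---|
| 1 | 15 | 1 | 14/15 = 0.933 |
| 2 | 14 | 2 | 12/15 = 0.800 |
| 3 | 12 | 2 | 10/15 = 0.667 |
| 4 | 10 | 2 | 8/15 = 0.533 |
| 5 | 8 | 1 | 7/15 = 0.467 |

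The Kaplan-Meier median is 5 days, against 3.0.

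If the six censoring times were entered as values, the mean would be (30 + 59)/15 = 5.9 days and the median (8th of 15) 5 days. The median agrees with Kaplan-Meier here only because every censoring time falls after it. The mean counts 59 days of non-clearance as time to clearance.

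**2. Does the ordinary summary respond to non-clearers?** Clearers' times follow one fixed pattern (2, 3, 3, 4, 4, 5, 5, 6, 6, 7, 7, 8, 9, 10, 12 days, thinned evenly), and k of 15 never clear.

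| k | n shown | Mean | Ordinary median | KM median, censored day 14 or 42 | KM median, censored day 4 |
|---|---|---|---|---|---|
| 0 | 15 | 6.07 | 6.0 | 6 | 6 |
| 3 | 12 | 6.08 | 5.5 | 7 | 6 |
| 5 | 10 | 6.10 | 5.5 | 8 | 6 |
| 6 | 9 | 6.11 | 6.0 | 9 | 7 |
| 7 | 8 | 6.00 | 5.5 | 12 | 6 |
| 8 | 7 | 6.14 | 6.0 | not reached | 7 |
| 12 | 3 | 6.00 | 6.0 | not reached | 6 |

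The ordinary mean and median barely move; only n falls. The Kaplan-Meier median moves clearly when non-clearers are followed to day 14 or later. It moves little when they are all censored by day 4.

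**3. How large is the gap?** Simulation of 4,000 trials of 15 patients per scenario, with a 30% daily chance of clearing among those who can clear, and last cultures on days 4 to 14 in those who never do:

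| Never cleared | Average ordinary median | Typical KM median | Typical within-trial gap | Trials with ordinary median lower |
|---|---|---|---|---|
| 13% | 2.6 | 3 | 0 days | 46% |
| 20% | 2.6 | 3 | 1 day | 62% |
| 30% | 2.6 | 4 | 1 day | 82% |
| 40% | 2.6 | 5 | 3 days | 93% |

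With last cultures on days 1 to 4 instead, the typical gap at 40% falls from 3 days to 1.

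**The case against.** The strongest reply is that the SAP already contains the right analysis. The Kaplan-Meier median keeps every uncleared patient in the risk set until the last assessment. A reader might infer from the descriptive sentence alone that the plan drops patients who never clear and will show fast clearance however many fail. The documents do not support that: the Kaplan-Meier paragraph follows in the same section, and its median lengthens or is not reached as followed non-clearers accumulate.

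Non-clearance is also visible elsewhere. SAP 7.1.1 puts n beside each mean and median, so 9 in a population of 15 is a visible warning. SAP 7.4.2.5 counts cultures that stayed positive, SAP 7.4.2.2 reports eradication with an exact interval, and the primary endpoint counts as a failure anyone not meeting the success criteria.

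It can also be said that the observed-values rule is worded for other variables, after separate rules for efficacy outcomes and dates, so its application here is an inference. And the size of the gap rests on assumed rates.

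Most of this stands and sets the severity. It does not remove the point. The rule in SAP 7.1.2 that keeps dropouts in efficacy denominators cannot repair a mean or median, which has no denominator in which to keep an absent value. The Kaplan-Meier estimate is introduced as an addition, so it neither replaces nor relabels the first summary. Counts of non-clearers in other tables do not correct a median labelled MITT.

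A claim that the ordinary median can never lengthen as more patients fail to clear would also go too far: in a sample this small, it rises if the fast clearers are the ones lost.

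**Conclusion.** The point holds as a minor one. The ordinary mean, SD and median of time to first negative blood culture are conditional on clearing but carry an MITT or PP label, and they do not respond systematically to the number of non-clearers. Under the assumptions above, the ordinary median is typically 0 to 1 day shorter than the Kaplan-Meier median at 13% to 30% never cleared, and about 3 days shorter at 40% when non-clearers are followed to days 4 to 14. These sizes are illustrative. The conclusion that the ordinary summary omits non-clearers rests on reading SAP 7.1.2 as applying here; entering censoring times as values would be wrong for a different reason.

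The harm is a misleading companion figure for a descriptive secondary endpoint. No analysis is missing, and the primary endpoint is untouched.

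**What to change.** Change SAP 7.4.2.3 only.

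1. Delete the descriptive-statistics sentence, or keep it labelled *among patients who cleared*, with the number not cleared shown beside it.
2. Name the Kaplan-Meier estimate as the summary for the MITT and PP populations.
3. Optionally, add the number and percentage with a negative culture by fixed study days, for example Days 2, 3, 4, 7 and 14, with uncleared patients in the denominator. This helps where non-clearers leave early and the Kaplan-Meier median moves little.

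Protocol 9.2.1.2 should stay as it is: its promise of a descriptive summary is met by the Kaplan-Meier estimate, and removing it would take away that section's commitment to report the endpoint. The cost is an edit to one SAP section and its table shell, with no new data.
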